14.1 Study Monitoring

Confidential and Proprietary

This document contains confidential and proprietary information on Smith & Nephew PLC and Smith & Nephew, Inc. and is only available to Smith & Nephew and its manufacturers. Without prior written approval of Smith & Nephew, the content cannot be replicated, printed totally/partially or disclosed in any other way, and anyone must use it as per the requirements, either expressed or implied by Smith & Nephew.

Study Protocol - Device	Smith+Nephew
A Prospective, Multi-center, Randomized Clinical Study to Evaluate the Safety and Effectiveness of Biosure Regenesorb Interference Screw in Arthroscopic Reconstruction of Cruciate Ligaments in Chinese Patients	Study No.: BIOSURE RG.SMD.PMA.2019.01
	Version: V2.0/July 3rd, 2020
	Page 51 of 74

Clinical study monitoring is an important means to ensure the quality of clinical study.

This study will be monitored by the Sponsor or by qualified personnel designated by the Sponsor. Qualified personnel may be employees of the Sponsor, or may be from a contract research organization (the agent of Sponsor). The Sponsor will monitor according to the monitoring frequency and the monitoring contents specified in the monitoring plan. The monitoring contents include and are not limited to the following aspects.

The Sponsor, the agent of Sponsor, EC and regulatory authorities can directly access the source documents, so as to verify and evaluate the clinical data submitted by the investigator to the Sponsor through the CRF.

The investigator is responsible for obtaining and maintaining complete health information of subjects recorded in the medical records (original documents). The raw data includes all original record information and certified copies of the original records (including clinical findings, observations, or other activities used for study reconstruction and evaluation in clinical study).

Prior to the implementation of the clinical agreement, the Sponsor performs qualification evaluation visits to each study site to ensure that all investigators have received the corresponding training and that their personnel, facilities and resources are sufficient to carry out this study.

Details can be found in the section of "Monitoring Plan" of this trial.

14.2 Audit of Sponsor

The objective of audit is to ensure the quality of the clinical trial project, ensure that the risk of the trial is controllable and evaluate whether the implementation of the trial is strictly in accordance with the trial protocol and the standard operating procedure of the Sponsor; audit also check whether all study guidelines and quality standards are implemented, promptly discover any careless mistake and errors, ensure the authenticity and reliability of clinical data, and data traceability, and promote the investigators, monitors, CRC to perform their work better, put forward meaningful suggestions for the trial, and guide the project to carry out better.

Participation in the study means acceptance of an audit to the study site, and is independent of the monitoring follow-up, so as to assess the compliance with the protocol, guidelines and regulations. The auditor designated by the quality control department or his/her representative will be responsible for such visits. The Sponsor has the right to require the sites with poor trial quality to perform rectification.

Confidential and Proprietary

This document contains confidential and proprietary information on Smith & Nephew PLC and Smith & Nephew, Inc. and is only available to Smith & Nephew and its manufacturers. Without prior written approval of Smith & Nephew, the content cannot be replicated, printed totally/partially or disclosed in any other way, and anyone must use it as per the requirements, either expressed or implied by Smith & Nephew.

Study Protocol - Device	Smith+Nephew
A Prospective, Multi-center, Randomized Clinical Study to Evaluate the Safety and Effectiveness of Biosure Regenesorb Interference Screw in Arthroscopic Reconstruction of Cruciate Ligaments in Chinese Patients	Study No.: BIOSURE RG.SMD.PMA.2019.01
	Version: V2.0/July 3rd, 2020
	Page 52 of 74

14.3 Laboratory Quality Control

The laboratories of each study site should establish a unified standard for laboratory test indicators, standard operating procedures and quality control procedures. For the laboratory test items, the national legal measurement units must be adopted, the items of the test reports must be complete (including date, test items, test results and their normal ranges). Special test item(s) must be tested by a special person.

15 Ethical issues and informed consent of clinical trial

15.1 Ethical Considerations and Ethical Approval

This clinical study must follow the Declaration of Helsinki, and should be carried out according to the clinical study standards and regulations related to medical devices issued by International conference on Harmonization (ICH) and China.

Investigators are responsible for obtaining written and dated approval from an Ethics Committee (EC) prior to enrolling subjects. This approval should include the protocol, the informed consent form, subject recruitment materials, advertising or any written information that will be provided to subjects.

Investigators are responsible for maintaining EC approval throughout the study by submitting progress reports (continuing review reports) at least annually and more often if requested by the EC.

Withdrawal of EC Approval: The Investigator shall report to the Sponsor within 5 working days if, for any reason, the EC withdraws approval to conduct the investigation. The report will include a complete description of the reason(s) for which approval was withdrawn.

Progress Reports: The Investigator is required to submit annual progress reports to the study Sponsor and to the reviewing EC. Reports must include the number of subjects, a summary of all follow-up evaluations, a summary of all adverse events, protocol deviations and a general description of the study progress.

Final Report: The Investigator will submit a final report to the Sponsor and to the EC within 3 months of completion of the study, termination of the study or termination of that Investigator's participation in the study.

Other Reports: Upon request of the Sponsor, NMPA or the EC, the Investigator shall provide

Confidential and Proprietary

This document contains confidential and proprietary information on Smith & Nephew PLC and Smith & Nephew, Inc. and is only available to Smith & Nephew and its manufacturers. Without prior written approval of Smith & Nephew, the content cannot be replicated, printed totally/partially or disclosed in any other way, and anyone must use it as per the requirements, either expressed or implied by Smith & Nephew.

Study Protocol - Device	Smith+Nephew
A Prospective, Multi-center, Randomized Clinical Study to Evaluate the Safety and Effectiveness of Biosure Regenesorb Interference Screw in Arthroscopic Reconstruction of Cruciate Ligaments in Chinese Patients	Study No.: BIOSURE RG.SMD.PMA.2019.01
	Version: V2.0/July 3rd, 2020
	Page 53 of 74

accurate, complete and current information.

Additional documents that require the Investigator obtain written and dated EC approval during the course of the study include:

- Protocol amendments (should not be implemented prior to EC approval)
- Informed consent form revisions (Sponsor reserves the right to review all revised informed consent forms prior to submission as they relate to the Sponsor's obligations)
- Protocol deviation report
- Adverse events described in Section 16 of this protocol
- All other documents as required by the EC

15.2 Informed consent

Investigators are responsible for obtaining and documenting the voluntary informed consent of the study subjects prior to conducting any study-related assessments per International Conference on Harmonization (ICH) and Good Clinical Practice (GCP) guidelines.

In obtaining informed consent, Investigators must adhere to GCP guidelines and to the ethical principles that have their origin in the Declaration of Helsinki.

Prior to beginning the study, the Investigator must obtain written and dated EC approval of the informed consent form. The informed consent form and any other written information provided to subjects should be revised whenever important new information becomes available that may be relevant to the subject's continued consent. All revised informed consent forms must have written and dated EC approval in advance of use.

The communications with the subject regarding informed consent process (initial and subsequent) will be documented in the medical record. Subjects should receive a copy of the initial signed and dated informed consent form (in the local language) prior to the subjects' participation in the study and any revised informed consent forms during the duration of the study.

Use of device without Informed Consent: No subject may be treated with a study device without prior Informed Consent. Such treatment constitutes a violation of NMPA regulations. The Investigator shall submit a report indicating the circumstances for the occurrence to Smith & Nephew and to the reviewing EC within five working days after the use occurs.

Confidential and Proprietary

This document contains confidential and proprietary information on Smith & Nephew PLC and Smith & Nephew, Inc. and is only available to Smith & Nephew and its manufacturers. Without prior written approval of Smith & Nephew, the content cannot be replicated, printed totally/partially or disclosed in any other way, and anyone must use it as per the requirements, either expressed or implied by Smith & Nephew.

Study Protocol - Device	Smith+Nephew
A Prospective, Multi-center, Randomized Clinical Study to Evaluate the Safety and Effectiveness of Biosure Regenesorb Interference Screw in Arthroscopic Reconstruction of Cruciate Ligaments in Chinese Patients	Study No.: BIOSURE RG.SMD.PMA.2019.01
	Version: V2.0/July 3rd, 2020
	Page 54 of 74

16 Adverse Event Reporting and Complaint

16.1 Definition

An adverse event is defined as any untoward medical occurrence in a clinical investigation in which a subject is administered a study device and which does not necessarily have a causal relationship with the device. An adverse event can therefore be any unfavorable and unintended sign (including an abnormal laboratory finding), symptom, or disease temporally associated with the use of study device, whether or not related to the study device.

Any events that occur newly or deteriorate in severity and frequency as compared with baseline conditions, or abnormal results found in the process of diagnosis, including abnormal laboratory findings, are included herein.

Note: The Sponsor collects the information on adverse events when the subjects sign the informed consent form.

The following are specific definitions of adverse events:

AE Adverse event - any untoward medical occurrence in a subject, regardless if there is a relationship between the AE and the device.

SAE Serious Adverse Event - an adverse event that:

A Serious Adverse Event is any AE that results in a death or a serious deterioration in the health of the subject during the clinical trial, including a life-threatening illness or injury, a permanent impairment of a body structure or a body function, in-patient hospitalization or prolongation of existing hospitalization, medical or surgical intervention to prevent permanent impairment of a body structure or a body function; or results in fetal distress, foetal death or congenital abnormality, congenital anomaly, etc.

ADE Adverse Device Effect – any untoward and unintended response to a medical device (This definition includes any event that is a result of a user error).

SADE Serious Adverse Device Effect – An adverse effect that has resulted in any of the consequences characteristic of a serious adverse event

UADE Unanticipated Adverse Device Effect - An “unanticipated adverse device effect” (UADE) is defined as any serious adverse effect on health or safety or any life-threatening problem or death caused by or associated with this device which was not previously identified in nature, severity, or

Confidential and Proprietary

This document contains confidential and proprietary information on Smith & Nephew PLC and Smith & Nephew, Inc. and is only available to Smith & Nephew and its manufacturers. Without prior written approval of Smith & Nephew, the content cannot be replicated, printed totally/partially or disclosed in any other way, and anyone must use it as per the requirements, either expressed or implied by Smith & Nephew.

Study Protocol - Device	Smith+Nephew
A Prospective, Multi-center, Randomized Clinical Study to Evaluate the Safety and Effectiveness of Biosure Regenesorb Interference Screw in Arthroscopic Reconstruction of Cruciate Ligaments in Chinese Patients	Study No.: BIOSURE RG.SMD.PMA.2019.01
	Version: V2.0/July 3rd, 2020
	Page 55 of 74

degree of incidence in the application of the device.

USADE Unanticipated Serious Adverse Device Effect - Serious adverse device effect which by its nature, incidence, severity or outcome has not been identified in the current version of the risk analysis report.

ASADE Anticipated Serious Adverse Device Effect - A serious adverse device effect which by its nature, incidence, severity or outcome has been previously identified in the risk analysis report.

DD Device Deficiency - An inadequacy of a medical device with respect to its identity, quality, durability, reliability, safety or performance; Device deficiencies include malfunctions, use errors, and inadequate labeling.

16.2 Treatment for Adverse Events

In the event of an adverse event, the Investigator and/or other professional personnel in attendance will provide whatever appropriate therapy for the event. Under all circumstances, a suspected adverse event relating to the study device should be provided the adequate medical treatment.

16.3 Reporting of adverse events

16.3.1 Investigator Adverse Event Reporting

All AEs will be categorized according to the investigator's clinical judgment as mild, moderate or serious based on the following definitions:

Mild: The subject is aware of the sign or symptom, but finds it easily tolerated. The event is of little concern to the subject and/or little clinical significance. The event is not expected to have any effect on the subject's overall health or well-being.

Moderate: The subject has discomfort enough to cause interference with or change in usual activities. The event is of some concern to the subject's health or well-being and may require medical intervention and/or close follow-up.

Serious: The adverse event interferes considerably with the subject's usual activities. The event is of definite concern to the subject and/or poses substantial risk to the subject's health or well-being. The event is likely to require medical intervention and/or close follow-up and may be incapacitating or life threatening. Hospitalization and treatment may be required.

Reporting of adverse events to regulatory authorities will be undertaken according to the provisions of NMPA and guidances.

Confidential and Proprietary

This document contains confidential and proprietary information on Smith & Nephew PLC and Smith & Nephew, Inc. and is only available to Smith & Nephew and its manufacturers. Without prior written approval of Smith & Nephew, the content cannot be replicated, printed totally/partially or disclosed in any other way, and anyone must use it as per the requirements, either expressed or implied by Smith & Nephew.

Study Protocol - Device	Smith+Nephew
A Prospective, Multi-center, Randomized Clinical Study to Evaluate the Safety and Effectiveness of Biosure Regenesorb Interference Screw in Arthroscopic Reconstruction of Cruciate Ligaments in Chinese Patients	Study No.: BIOSURE RG.SMD.PMA.2019.01
	Version: V2.0/July 3rd, 2020
	Page 56 of 74

For all UADEs, SAEs, USADEs, SADEs and device deficiencies which may lead to a SAE, that occur during the course of the clinical study, once the investigator knows, he/she must take appropriate treatment measures for the subjects and report to the Sponsor and the study site of hospital immediately.

The administrative department of medical device clinical trials shall send written reports to corresponding EC, the food and drug administration of the concerned province or autonomous region or municipality directly under the central government, and the competent authority of health and family planning within 24h. Regarding adverse events of death, study sites and investigators should provide all required data to the corresponding Ethics Committees and Sponsor.

Details of all adverse events or device deficiency must be recorded on the adverse event/device deficiency forms provided and faxed/e-mailed to the contact of Sponsor where possible at the time of reporting. Please keep the fax report or print an email as a record of the time limit. The contact details are shown in the Section “1. Sponsor Information” of the protocol.

The Investigator must submit a detailed report that will identify the description of symptoms, classification of the event, date of onset, severity, treatment, and outcome. Supporting medical records may be obtained as an adjunct to an adverse event report and placed in the subject’s study file.

During the clinical study, all serious and non-serious adverse events should be followed up to determine the final outcome.

All SAEs, which haven’t been resolved at the end of the study or when the subjects withdraw prematurely from the study, must be followed up until one of the followings is achieved:

- The event is resolved
- Achieve stable state
- Reasonable explanation is provided
- Lost to follow-up or death
- The event restores to the baseline level (if the baseline value is available)
- When it is impossible to obtain more information (the patient or medical staff refuses to provide more information, and there is evidence showing that the patient is still lost to follow-up after the medical staff tries his/her best)

Once a subject has completed the study, the investigator should follow up for outcomes on all AEs

Confidential and Proprietary

This document contains confidential and proprietary information on Smith & Nephew PLC and Smith & Nephew, Inc. and is only available to Smith & Nephew and its manufacturers. Without prior written approval of Smith & Nephew, the content cannot be replicated, printed totally/partially or disclosed in any other way, and anyone must use it as per the requirements, either expressed or implied by Smith & Nephew.

Study Protocol - Device	Smith+Nephew
A Prospective, Multi-center, Randomized Clinical Study to Evaluate the Safety and Effectiveness of Biosure Regenesorb Interference Screw in Arthroscopic Reconstruction of Cruciate Ligaments in Chinese Patients	Study No.: BIOSURE RG.SMD.PMA.2019.01
	Version: V2.0/July 3rd, 2020
	Page 57 of 74

classified as possibly/definitely related to the investigational product and all serious adverse events until a final outcome can be determined or the end of the whole study (last subject last visit), whichever comes first.

During the subject's participation in the trial, any event that caused hospitalization or prolonged hospitalization must be reported as a serious adverse event, unless because of:

- Hospitalization for social reasons rather than adverse events
- Surgery or operation that has been planned prior to participation in the trial (must be recorded in the original medical record and CRF)

16.3.2 Sponsor Adverse Event Reporting

For the serious adverse events and the device deficiencies that may cause serious adverse events, Smith & Nephew should report to the food and drug administration and the competent authority of health and family planning at the same level where the device is registered within 5 workdays after being informed. Smith & Nephew should also inform other study sites and investigators that participate in the trial, and timely inform the Ethics Committee of such study site through its administrative department for clinical trial of medical device.

16.3.3 Causal relationship between AEs and the device and its evaluation criteria

The AE is set to be related to the device in case of being "extremely probably related", "definitely related" and "probably related"; in case of other classification, the AE is set to unrelated to the device.

Classification	Description
Definitely un-related	The AE is identified as a result of a concomitant disease or the effects of another device/drug and is not related to the investigational product.
Probably un-related	The AE is more probably caused by other reasons and will not be improved or its prognosis is difficult to be judged after device withdrawal. Its recurrence is not found or difficult to be judged after device reuse.
Probably related	The occurrence of the AE meets the reasonable time sequence upon device use. The AE may be caused by the device or other reasons. It is improved

Confidential and Proprietary

This document contains confidential and proprietary information on Smith & Nephew PLC and Smith & Nephew, Inc. and is only available to Smith & Nephew and its manufacturers. Without prior written approval of Smith & Nephew, the content cannot be replicated, printed totally/partially or disclosed in any other way, and anyone must use it as per the requirements, either expressed or implied by Smith & Nephew.

Study Protocol - Device	Smith+Nephew
A Prospective, Multi-center, Randomized Clinical Study to Evaluate the Safety and Effectiveness of Biosure Regenesorb Interference Screw in Arthroscopic Reconstruction of Cruciate Ligaments in Chinese Patients	Study No.: BIOSURE RG.SMD.PMA.2019.01
	Version: V2.0/July 3rd, 2020
	Page 58 of 74

	after device withdrawal.
Extremely probably related	The occurrence of the AE meets the reasonable time sequence upon device use. The AE is more reasonably attributed to the used device than other reasons. It is improved after device withdrawal.
Definitely related	The occurrence of the AE meets the reasonable time sequence upon device use. The AE is more reasonably attributed to the used device than other reasons. The AE mode is consistent with the previously known mode caused by the device. The AE is improved after device withdrawal but appears after device reuse.

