6.1 Trial objective

The objective of this study is to compare the safety and effectiveness of Biosure Regenesorb Interference Screw versus the control device in patients requiring repair or reconstruction of cruciate ligaments (including anterior cruciate ligament (ACL) and posterior cruciate ligament (PCL)). The trial results will be used for registration of Biosure Regenesorb Interference Screw in China.

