6.2 Study contents

This clinical trial is designed to be a prospective, multi-center, randomized, evaluator-blinded, parallel-controlled, non-inferiority trial. The primary efficacy endpoints are not inferior to the control group. The Biosure Regenesorb Interference Screw and BIOSURE HA Interference Screw are used in the trial and control groups, respectively, to evaluate the safety and effectiveness of the investigational medical device Biosure Regenesorb Interference Screw in clinical repair or reconstruction of knee cruciate ligament rupture or tear.

The subjects complying with the criteria for inclusion in this clinical trial will receive 24-month follow-up after being treated with the investigational product or the control product. The following endpoints will be recorded and evaluated: Lysholm score, IKDC score, Drawer test, Lachman test and imaging evaluation results at the follow-up visit at month 6, 12 and 24 after the operation, respectively, incidence and frequency of ADEs, AEs, and device deficiency throughout the trial and reoperation rate.

7 Background of Clinical Trial

The knee becomes one of the most injured joints due to its anatomical structure and particular function in human body. According to the statistics, there are 200,000 ACL rupture cases per year in the United States, including 100,000 requiring ACL reconstruction. An epidemiological investigation in sport injury showed that the total incidence of ACL injury is 0.47% in China. PCL injury are relatively infrequent. As reported in foreign literature, PCL injury has an incidence of 3% in the common population and account for 20% of knee ligament injury. No similar reports are found in China.

The ACL femoral attachment, located at the posterior part of the medial side of the lateral femoral

Confidential and Proprietary

This document contains confidential and proprietary information on Smith & Nephew PLC and Smith & Nephew, Inc. and is only available to Smith & Nephew and its manufacturers. Without prior written approval of Smith & Nephew, the content cannot be replicated, printed totally/partially or disclosed in any other way, and anyone must use it as per the requirements, either expressed or implied by Smith & Nephew.

Study Protocol - Device	Smith+Nephew

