10.1.6.2 Safety evaluation contents

Safety evaluation includes the following contents:

- Incidence (%) and frequency (number of events) of AEs related to device;
- Incidence (%) and frequency (number of events) of adverse events;

Confidential and Proprietary

This document contains confidential and proprietary information on Smith & Nephew PLC and Smith & Nephew, Inc. and is only available to Smith & Nephew and its manufacturers. Without prior written approval of Smith & Nephew, the content cannot be replicated, printed totally/partially or disclosed in any other way, and anyone must use it as per the requirements, either expressed or implied by Smith & Nephew.

Study Protocol - Device	Smith+Nephew
A Prospective, Multi-center, Randomized Clinical Study to Evaluate the Safety and Effectiveness of Biosure Regenesorb Interference Screw in Arthroscopic Reconstruction of Cruciate Ligaments in Chinese Patients	Study No.: BIOSURE
	RG.SMD.PMA.2019.01
	Version: V2.0/July 3rd, 2020
	Page 33 of 74

- Incidence (%) and frequency (number of events) of device deficiencies;
- Reoperation rate.

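### The device-causality scale allows a reaction to the control screw to be graded either unrelated or related, because one row is tied to the investigational product alone

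*Combined protocol and SAP*

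**What the plan says.** Section 16.3.3 sets five grades and collapses them into two classes. The three related grades count as device-related; "in case of other classification, the AE is set to unrelated to the device".

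The lowest grade is for an AE put down to a concomitant disease or "the effects of another device/drug and is not related to the investigational product". The middle grade (*probably related*) says "The AE may be caused by the device or other reasons". The two highest grades weigh the used device against other reasons.

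The protocol has separate terms for the two screws. Section 6.2 follows subjects "after being treated with the investigational product or the control product", and sections 10.1.2 and 12.5 draw the same contrast.

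The first item in section 10.1.6.2 is "Incidence (%) and frequency (number of events) of AEs related to device". Section 6.1 states the aim as to "compare the safety and effectiveness of Biosure Regenesorb Interference Screw versus the control device". Section 10.1.6.1 makes the safety analysis descriptive, without formal tests.

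Two other rules use investigational-only wording. After a subject completes, section 16.3.1 requires follow-up of AEs "classified as possibly/definitely related to the investigational product and all serious adverse events until a final outcome can be determined" or the whole study ends. Section 12.9.3 defines the safety set as subjects randomised to the investigational device.

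**The concern.** In a control subject, the BIOSURE HA screw is a device other than the investigational product. Taken at its words, the lowest grade is open to an AE caused by that screw, and the two-class rule then counts the AE as not device-related. The same kind of AE caused by the Regenesorb screw cannot enter the class by this route.

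If some sites read the row that way, the control arm's device-related incidence would be too low and the investigational screw would look worse by comparison. The control figure is what a reader uses to judge whether the investigational figure is acceptable.

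The design offers little to catch such an error. Section 10.1.3.2 describes blinding only for the rater who completes the scoring, and no blinded review of causality is described. Section 18 says that hospital records usually hold no causality judgment, so the sponsor's form is the source document. A grade entered there may have nothing independent to be checked against.

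**Working it through.** **Step 1. One control-arm event, taken through the rows.** Take an AE caused by the BIOSURE HA screw in a control subject.

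| Row in 16.3.3 | Device it refers to | Does the event fit? |
|---|---|---|
| Definitely un-related | the investigational product, with another device allowed as the cause | Yes, on the words |
| Probably un-related | device withdrawal or reuse, no arm named | No, if the screw is the likely cause |
| Probably related | the device, no arm named | Yes |
| Extremely probably related | the used device | Yes |
| Definitely related | the used device | Yes, if the pattern is a known one |

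The event fits the lowest grade and at least one related grade. Nothing in 16.3.3 says which screw is the device for a control subject, or which row takes precedence. For a Regenesorb reaction in the investigational arm the first row fails, so there is no conflict. The surgery scale in 16.3.4 does not have the problem, because both arms have the operation.

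**Step 2. Reach of the follow-up rule.** While a subject is in the study, 16.3.1 requires every AE, serious or not, to be followed to outcome in both arms. After completion the narrower rule applies, and serious AEs remain covered in both arms. What is left out is a control-screw AE that is non-serious and still unresolved when the subject completes. Incidence and event counts do not depend on this.

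**Step 3. Size.** The documents give no device-related event rate, so there is no plan figure to reproduce. The only stated input is 70 subjects per group (section 12.2.1). Two quantities must be assumed:

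- p, the true screw-reaction rate, taken as equal in both arms;
- m, the share of control-screw reactions graded *definitely un-related*.

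Expected counts are 70 × p in the investigational arm and 70 × p × (1 − m) in the control arm. The spurious excess is 100 × p × m percentage points.

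| p | Investigational count | Control count: m = 0 / 0.5 / 1 | Spurious excess, points: m = 0 / 0.5 / 1 |
|---|---|---|---|
| 2% | 1.4 | 1.4 / 0.7 / 0 | 0 / 1 / 2 |
| 5% | 3.5 | 3.5 / 1.75 / 0 | 0 / 2.5 / 5 |
| 10% | 7 | 7 / 3.5 / 0 | 0 / 5 / 10 |

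The table shows direction and scale only. The documents support no particular value of p or m.

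**The case against.** The strongest reply is that this is loose wording in one row. One scale serves all subjects. Its heading, its two-class rule and its other four rows speak of the device without naming an arm. To misgrade a control-screw reaction, an investigator who believes the implanted screw caused it would have to call it definitely unrelated on a scale about the device. In context, another device most naturally means something other than the one being assessed.

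The protocol also uses investigational device loosely elsewhere. Read literally, 12.9.3 would leave the control arm without a safety set, and 10.1.4.4 would make every control subject eligible for withdrawal for not receiving the investigational device. Section 16.1 has arm-neutral definitions of an AE and an adverse device effect. All AEs, device deficiencies and reoperations are counted whatever this row says.

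Much of this stands. A reader might infer that the two arms are attributed by different rules. The documents do not support that: the scale is common to both arms, and most of it covers either screw. The reply does not remove the conflict. Loose usage elsewhere is not a definition, and the text does not instruct a site to prefer the sensible reading. The row is an operative rule behind a listed safety indicator.

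**Conclusion.** The scale in 16.3.3 contradicts itself for the control arm, and a BIOSURE HA reaction can be graded either way. This could understate device-related AEs in the control arm. The amount cannot be estimated from the documents, and it is zero if sites follow the used-device wording. The follow-up rule in 16.3.1 has the same wording but affects only non-serious AEs unresolved at a subject's completion. The safety set in 12.9.3 needs the same correction.

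A reader might go further and infer that every control-screw reaction would be lost, then test 7/70 against 0/70 (two-sided Fisher p = 0.013). That needs an assumed 10% rate and the least sensible reading at every site, and the plan makes no formal safety test. Nothing shows that any event has been or will be misgraded.

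The primary endpoint, sample size and success criterion are unaffected. Any error would run against the investigational screw, so it would not favour the registration claim. The correction is worth making because it is specific and costs almost nothing.

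**What to change.** - In 16.3.3, refer in all five rows to *the study screw implanted in that subject (investigational or control)*, and define another device as a non-study device.
- Use the same arm-neutral term in the post-completion follow-up rule of 16.3.1, in the safety set definition in 12.9.3 and on the AE form.
- If grades have already been entered, re-check them in both arms under the same wording. Regrading the control arm alone could create the differential attribution that the change is meant to prevent.

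The cost is a few words in three sections and one form, plus a short re-check if grades exist. It needs no extra subjects or visits.
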